3.1 Hemiplegic patients with first onset stroke were treated with abdominal acupuncture combined with upper limb rehabilitation training to observe the recovery of upper limb motor function, the muscles synergy monitored by sEMG, local brain area activation by fMRI and the integrity of pyramidal tract of cerebral white matter.

3.2 To analyze the changes of upper limb motor function the relationship between the changes and sEMG or brain fMRI

3.3 to explore the possible mechanism of abdominal acupuncture combined with upper limb rehabilitation training on brain plasticity of upper limb motor function recovery in hemiplegic patients with stroke.

4. Reporting Units and Research Units

Reporting unit: Rehabilitation Department of Guangdong Provincial Hospital of Chinese Medicine

Address: [name]

Research Director: [name] e-mail:[contact]

Clinical Auditor: [name] e-mail:[contact]

Head of Clinical Research Unit: Rehabilitation Department of Guangdong Provincial Hospital of Chinese Medicine

Address: [name]

Research Director: [name] e-mail:[contact]

Participating Units:

Rehabilitation Department of Guangdong Provincial Hospital of Chinese Medicine

Director: [name]

Chinese University of Hong Kong

Director: [name]

5. Research Design

5.1 Case selection: 66 patients diagnosed with initial stroke by CT/MRI and hospitalized in rehabilitation department of our hospital who meet the inclusion criteria will be included.

5.2 Random method: Patients met the inclusion criteria will be randomized into 3 groups by MATLAB stratified randomization software:

Treatment group A: abdominal acupuncture +upper limb rehabilitation training, 22 cases;

Treatment group B: Sham abdominal acupuncture +upper limb rehabilitation training, 22 cases;

Control group : upper limb rehabilitation training only , 22 cases.

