Sample size calculation: Using the SAMPSIZEPWR function calculation of MATLAB software Statistic Toolbox (Statistics Toolbox) to calculate, it is assumed that Fugl-meyer assessment (FMA) is the outcome index, and the FMA before rehabilitation training is also assumed to be 30 ± 10 (average \pm Standard deviation), the FMA after rehabilitation training is 37 (average). The amount of effect between groups is ~ 0.7 . If 0.8 of the statistical verification force is required, the sample size is 19 cases calculated by T-Test. Taking some uncontrollable factors that may causing dropping off into consideration, each group increases 3 cases with a 15% fall rate. Each group will include 22 cases.

5.3 Inclusion Criteria:

- ① First onset stroke, Left hemiplegia, Right-handed, and diagnosed by brain CT or MRI;
- ② Age 35 to 75 years old;
- ③ Course of disease 0.5 to 3 months with stable vital signs;
- ④ No cognitive impairment. Can understand and execute commands. MMSE score more than 7 points. ;
- ⑤ Can control the sitting balance. Brunnstrom stage of hemiplegic upper limb and hand is IV or V , Fugl-Meyer Motor Assessment score of upper limb 20-50 point;
- ⑥ Agree to sign the informed consent;
- ⑦ Unilateral neglect.

5.4 Exclusion Criteria:

- ① Recurrent stroke, subarachnoid hemorrhage, brain tumors patients;
- ② Contraindication to undergo a 3T MR imaging;
- ③ Claustrophobia;
- ④ Have severe heart, hepatic or renal failure;
- ⑤ Don' t cooperate with the treatment;
- ⑥ Have participated in other clinical trails recently.

5.5 Treatment Method:

Treatment group A: abdominal acupuncture +upper limb rehabilitation training;

Treatment group B: Sham abdominal acupuncture +upper limb rehabilitation training;

Control group : upper limb rehabilitation training only .

All the treatments above last for 30mins a time, once a day, five times a week, totally 4 weeks.

Upper limb Rehabilitation Training programme is based on the recommendations of the American AHA-ASA-2016-Stroke Rehabilitation Guideline , including instrumental activities of daily life training and upper limb operation therapy.

A: Instrumental activities of daily life training:

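### Inclusion item 7 names unilateral neglect without a negation, so the protocol can be read as requiring neglect in all 66 patients or in none

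*Protocol*

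**What the plan says.** Protocol 5.3 lists seven inclusion criteria. The seventh and last is "Unilateral neglect", with no verb, negation, instrument or threshold. The next line of the protocol is the heading of 5.4, Exclusion Criteria.

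The list is operative. Section 5.1 takes hospitalized patients with a first stroke "who meet the inclusion criteria will be included", and 5.2 states that "Patients met the inclusion criteria will be randomized into 3 groups". The sample size paragraph fixes the numbers: "Each group will include 22 cases".

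Three other eligibility lines bear on how item 7 should be read:

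- 5.3 item 4 writes its negation out: "No cognitive impairment".
- 5.3 item 1 uses bare nouns for things a patient must have: "First onset stroke, Left hemiplegia, Right-handed, and diagnosed by brain CT or MRI".
- 5.4 item 3 uses a bare noun for something a patient must not have: "Claustrophobia".

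The purpose in 3.1 describes the population only in general terms ("Hemiplegic patients with first onset stroke were treated with abdominal acupuncture combined with upper limb rehabilitation training"). Purpose 3.3 and the SAP title likewise speak of hemiplegic stroke patients without mentioning neglect.

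**The concern.** An eligibility line should not be open to opposite readings. Item 7 can be taken as a requirement that neglect be present, or as an exclusion that lost its negation or landed on the wrong side of the 5.4 heading. These readings select patients with no overlap on this characteristic.

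Eligibility decides who is enrolled and to whom the result applies. If neglect is required, the findings cover only patients with neglect, while the purpose and SAP title are phrased for hemiplegic stroke patients in general. If neglect bars entry, the printed list states the reverse of the rule. In either case, two screeners could apply the item differently, and a reader could not reproduce the selection or say which population the fMRI, sEMG and motor results describe.

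**Working it through.** The question is one of wording, so the check consists of confirming the planned numbers, stating what each reading implies, and searching the documents for anything that decides between them.

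**Planned numbers.** The sample size paragraph gives 19 per group plus 3 for dropout: 19 + 3 = 22. With three groups (5.2), 3 × 22 = 66, which matches 5.1.

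**What each reading implies.**

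| Reading of item 7 | Patients with neglect, per group | In total |
|---|---|---|
| Literal: neglect required | 22 of 22 | 66 of 66 |
| Negation lost, or exclusion misplaced | 0 of 22 | 0 of 66 |

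A third reading, that neglect is merely permitted, would allow any number from 0 to 66. It does not fit an item in a list of conditions to be met.

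**Places where an answer could lie.**

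- Background and purpose (3.1 to 3.3): neglect is not mentioned. For the purpose this is weak evidence, since left hemiplegia, a clear requirement, is not mentioned there either.
- Exclusion criteria (5.4, six items): neglect is not mentioned, so the list neither confirms nor contradicts item 7.
- Screening assessments (5.6, part 1): only the MMSE and Brunnstrom staging are named. A neglect test might have shown which way the item works, but there is none. Its absence does not decide the matter, because an exclusion would need checking just as a requirement would.
- Outcome measures (5.6, parts 2 and 3): no measure of neglect.
- SAP: neglect is not mentioned in the title or the analysis paragraph.

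The word therefore occurs once in the supplied text, in item 7 itself, and no second mention exists to resolve it.

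**Form and position of the line.** Item 4 shows that this list can write a negation when it means one, which favours the literal reading, as does the placement under the inclusion heading. The bare noun form is uninformative: it serves for a requirement in 5.3 item 1 and for an exclusion in 5.4 item 3. The position, last before the exclusion heading, is where a misplaced exclusion could easily sit. These cues point in different directions.

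**What cannot be computed.** The documents give no figure linking neglect to Fugl-Meyer, fMRI or sEMG results, so no effect on the outcomes can be calculated. All three groups are selected by the same list, so no bias in the between-group comparison follows from the ambiguity.

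**The case against.** The strongest reply is that there is no contradiction on the page. A bare item under an inclusion heading is a requirement, just as left hemiplegia is, and item 4 shows that the authors wrote a negation when they meant one. The comparison with claustrophobia is weak, because that item takes its meaning from its own heading. On this view, the doubt comes from a reader's expectation that neglect would be an exclusion. It can be added that a purpose statement is normally broader than the eligibility list: age range, right-handedness and Brunnstrom stage are absent from it too. Since no bias is shown and nothing in the sample size or SAP depends on neglect, the matter could be rated as minor.

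Part of this stands. The literal reading is the plain one by placement, the silence of the purpose proves little, and the 66 and 0 counts restate all and none without measuring harm. The omission of any neglect assessment from 5.6 does not rescue either reading.

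It does not remove the problem. If the literal reading is intended, the trial requires a specific condition that it never mentions again, never says how to confirm, and does not carry into its stated target population. If it is not intended, the eligibility list is wrong as printed. Text extraction could in principle have lost a word, but the line has its number and full stop and shows no gap or redaction. The sponsor can check the source file at once.

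**Conclusion.** The concern holds. Item 7 is an operative eligibility rule whose wording admits opposite readings, 66 of 66 patients with neglect or 0 of 66, and nothing in the protocol or SAP text decides between them. It must be corrected because it determines who is studied and to whom the conclusion applies.

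The conclusion is limited to applicability and reproducibility. It uses no outside figure and makes no assumption about which rule was intended. It rests on the supplied text being complete at item 7.

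**What to change.** The sponsor should state which rule was meant and reconcile 5.3 item 7 with 5.4 and the purpose. This review does not choose between the rules.

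- If neglect was meant to bar entry, add the negation to item 7 or move the line to 5.4.
- If neglect is required, name that population in the purpose, limit the conclusion to it, and add to the screening assessments in 5.6 how neglect is confirmed.

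The cost is a short amendment to one eligibility line, with matching text elsewhere if neglect is required. Records of any patients already screened would have to be reviewed against the clarified item. If neglect is truly required, the trial can no longer claim to cover hemiplegic stroke patients in general.

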Extend elbow (side): Subject attempts to reach across the table by extending the elbow (to the side).Extend elbow (to the side), with weight: Subject attempts to push the sandbag against outer wrist joint across the table by extending the elbow.Extend elbow (to the side), with weight: Subject attempts to push the sandbag against outer wrist joint across the table by extending the elbow. Hand to box (front): Subject attempts to place hand on the box.Pick up paper clip (front): Subject attempts to pick up paper clip by using a pincer grasp.Stack 3 checkers and flip 3 cards.Turning the key in the lock,fold towel,pick up the basket by grasping the handle and place it on the beside

table. Treatment Duration: 45 minutes a session, once a day, 5 times a week for 4 weeks.

B: Upper limb operation therapy:

According to the patient's specific situation, take the routine operation treatment. It includes the training of shoulder blades loosening, the active assistant and active training of the side upper limb, the joint activity training of the upper limb, the upper extremity training, and the grasping and opening of the side finger. Mainly with the side training, but also included a small number of contralateral auxiliary side training. Treatment time: 30 minutes/times, 1 times/day, 5 days/week, total 4 weeks.

5.6 Evaluation Method:

(1) Screening Assessment

Simple intelligent mental state scale (MMSE), and Brunnstrom upper limb movement staging will be evaluated once when included.

(2) Primary Outcome Measure:

Functional magnetic resonance imaging (fMRI) and surface electromyography (sEMG) are the two primary outcome, which will be tested before and 4 weeks after treatment, twice totally.

(3) Secondary Outcome Measure:

Wolf Motor Function Test; Brunnstrom staging of upper limb movement; Fugl-Meyer Motor Assessment of upper limb; Modified Barthel Index.

Time Frame: Before treatment, 2 weeks and 4 weeks after treatment, 3 times totally.

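### The only sample size calculation is a before-after calculation for FMA, a secondary outcome; the two primaries, fMRI and sEMG, have no sizing, operational variable, between-arm contrast or error-control rule

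*Protocol*

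**What the plan says.** **Primary outcomes.** Protocol section 5.6 (2) states "Functional magnetic resonance imaging (fMRI) and surface electromyography (sEMG) are the two primary outcome", measured twice. FMA appears in section 5.6 (3) among the secondary outcomes: "Fugl-Meyer Motor Assessment of upper limb; Modified Barthel Index".

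**Sample size.** The calculation in section 5.2 takes a different outcome: "it is assumed that Fugl-meyer assessment (FMA) is the outcome index". Its inputs are a mean of 30 with SD 10 before rehabilitation training, and then "the FMA after rehabilitation training is 37 (average"). It continues "The amount of effect between groups is ~ 0.7" and, for power 0.8, "the sample size is 19 cases calculated by T-Test". Three cases per group are added for 15% dropout, giving 22 per group and 66 in all. Alpha and sidedness are not stated.

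**Arms.** Section 5.5 gives upper limb training to all three arms. The third is described as "Control group : upper limb rehabilitation training only"; the other two add abdominal or sham abdominal acupuncture.

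**What the primaries are meant to show.** Section 3.1 mentions muscle synergy from sEMG, and "local brain area activation by fMRI and the integrity of pyramidal tract of cerebral white matter".

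**Analysis.** The SAP assigns a t-test to measurement data, repeated-measures analysis of variance and a chi-square test to counting data, and SPM8 to the images. It does not say whether the t-test is within or between arms, or which of the three pairs of arms it compares.

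**The concern.** Two things do not fit together.

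First, the outcome that was sized is not primary, and the outcomes that are primary were not sized. The stated power of 0.8 therefore says nothing about fMRI or sEMG.

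Second, the FMA calculation does not describe the comparison it names. A rise from 30 to 37 after training is a gain over time. Since the control arm also trains, that gain is not the advantage of acupuncture over sham or over training alone. A reader who takes the between-groups label at face value will believe that the arm comparison has 80% power when no input supports this.

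Because the variable, the contrast and alpha are all unstated for the primaries, the plan also does not say which result would count as the trial's primary result. That choice would be left until after the data are seen.

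**Working it through.** **Inputs.** From section 5.2: mean 30 before and 37 after, SD 10 before, power 0.8, n = 19, dropout 15%. Assumed, because not stated: alpha 0.05 two-sided; SD 10 after training as well; and, for between-arm power, a true difference between two arms of 7 points. All powers use the noncentral t distribution.

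**1. Reproducing 19.** d = (37 − 30)/10 = 0.7. For a one-sample or paired t-test the noncentrality is d√n, with n − 1 degrees of freedom.
- n = 18: 0.7 × √18 = 2.97, power 0.799.
- n = 19: 0.7 × √19 = 3.05, power 0.82.

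So 19 is the smallest n that reaches 0.8. For a before-after test this needs SD 10 to be the SD of change. With equal SDs, the SD of change is 10√(2(1 − r)), where r is the before-after correlation; it equals 10 only at r = 0.5. Section 5.2 gives 10 as the SD before training.

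**2. The same d as a two-sample test on final scores.** The noncentrality is d√(n/2), with 2n − 2 degrees of freedom.

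| n per arm | Noncentrality | Power |
|---|---|---|
| 19 | 0.7 × √9.5 = 2.16 | 0.556 |
| 22 | 0.7 × √11 = 2.32 | 0.621 |
| 33 | 0.7 × √16.5 = 2.84 | 0.7997 |
| 34 | 0.7 × √17 = 2.89 | 0.812 |

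The requirement is 34 per arm.

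**3. Could 19 per arm be a between-arm number at another alpha?** At two-sided 0.10 (equivalently one-sided 0.05) the two-sample requirement is 26. At one-sided 0.10 it is exactly 19 (power 0.803; 0.786 at 18). The documents state none of these levels.

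**4. Could the analysis recover the power?** Change scores have d = 0.7/√(2(1 − r)). Baseline adjustment has d = 0.7/√(1 − r²), with 2n − 3 degrees of freedom. Power at 19/22 per arm, two-sided 0.05:

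| r | Change scores | Baseline-adjusted |
|---|---|---|
| 0.5 | 0.56/0.62 | 0.68/0.75 |
| 0.6 | 0.65/0.72 | 0.75/0.81 |
| 0.7 | 0.77/0.83 | 0.84/0.89 |

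For 80% power, r must be about 0.72 (19) or 0.67 (22) with change scores, and 0.66 or 0.59 with adjustment. Neither document states a correlation or an adjustment. If the difference between arms were 5 points (an assumption), power on final scores would be 0.32/0.37.

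**5. Which n applies.** 19 × 1.15 = 21.85, rounded to 22, is how section 5.2 arrives at its total. With 15% loss, 22 × 0.85 = 18.7. The planned evaluable number is therefore about 19 per arm, and the figures for 22 hold only without loss.

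**6. The primaries.** No sample size can be computed for fMRI or sEMG, because no variable, effect, SD or alpha is given. Sections 3.1 and 5.6 (2) and the SAP together supply constructs, occasions and software. They do not supply a region, muscle, task or summary value, a pair of arms, or a rule for two primaries and three possible pairs.

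**The case against.** **Other readings of 19.** The strongest objection is that 19 does not prove a before-after test. A plain two-sample test also gives 19 per arm at one-sided 0.10, and a correlated or adjusted analysis could reach 80% at the conventional level. This stands in part. A reader might infer that a between-arm test with 19 per arm reaches 80% only with a correlation near 0.72 or 0.66. That holds only at two-sided 0.05, which the documents do not state. The before-after reading remains the better one, because the inputs in section 5.2 are before and after means. Whichever reading is meant, alpha, correlation and between-arm difference are missing.

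**Measures are named.** It is also fair to say that the primaries are not wholly undefined: section 3.1 names constructs, section 5.6 (2) gives occasions and the SAP names SPM8. So it would be too strong to say that the plan has no measure at all. What is missing is an operational variable that a t-test could be applied to.

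**Exploratory aims.** Section 3.3 speaks of exploring a mechanism. But section 5.6 still designates two primaries and section 5.2 still claims power 0.8. If exploration is intended, the labels should say so.

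**Null results.** A non-significant result would not show absence of effect even at 80% power; that depends on the confidence interval. The defect is narrower: the stated 0.8 gives no assurance about the arm comparison.

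**Sham.** A reader might infer that acupuncture versus sham isolates the effect of needling. The documents do not describe the sham procedure, so they do not support that.

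**Conclusion.** The point holds, and the text needs correcting. Two parts rest on the documents alone: the sized outcome is secondary while the primaries are unsized, and an effect labelled as between groups is built from a before-after gain under training common to all arms. So does the absence of an alpha, an operational primary variable, a between-arm contrast and a multiplicity rule.

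The size of the power gap is conditional. For a 7-point difference between two arms, SD 10 and two-sided 0.05, unadjusted power is about 0.56 at the planned evaluable number, against the stated 0.8, and 34 per arm would be needed.

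A reader might infer that the trial's FMA power is 0.56. The documents do not support that as a fact, since no between-arm difference is given: a smaller difference lowers the power, and a well-correlated, baseline-adjusted analysis raises it. Nor can any power figure, high or low, be attached to fMRI or sEMG.

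**What to change.** **(1) Section 5.2.** State that the calculation concerns FMA, a secondary outcome, and is a before-after calculation. State the alpha and whether SD 10 is the SD of change. Add that, at two-sided 0.05 and for an assumed 7-point difference between two arms, unadjusted power is about 0.56 with the 19 evaluable per arm planned after dropout, and 0.62 only if all 22 are evaluable. Claim no power for fMRI or sEMG. Claim more for FMA only with a specified adjusted or change-score analysis, a justified correlation and a justified between-arm difference.

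**(2) Section 5.6 (2) and the SAP, before data are seen.** Choose one of two routes.
- Keep fMRI and sEMG primary. Name one measure per modality at the post-treatment assessment, and clarify whether that assessment falls at the end of the four-week course or four weeks after it. Name one primary between-arm contrast (for example, acupuncture versus sham, with the sham described) and an error-control rule such as 0.025 per modality. Label all other measures and contrasts secondary or exploratory.
- Or make FMA the single primary, with a named contrast and a baseline-adjusted analysis, and label fMRI and sEMG mechanistic, which fits section 3.3.

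**Cost.** Wording only, no added patients. The stated power becomes less favourable. The first route brings a stricter threshold (illustrative unadjusted power at d = 0.7 and alpha 0.025: 0.44 with 19 per arm, 0.50 with 22), and fMRI and sEMG remain without a size calculation. Under the second they lose primary status, and 80% for FMA still needs a 7-point difference between arms and a correlation of about 0.66 with 19 evaluable per arm (0.59 with 22).

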Using fMRI and sEMG to Evaluate the Effects and Mechanism on Abdominal Acupuncture Combined With Upper Limb Rehabilitation Training on Brain Plasticity of Hemiplegic Patients With Stroke

Head of Clinical Research Unit: Guangdong Provincial Hospital of Chinese Medicine

Director of Clinical Research: [name]

Clinical Research Participating Unit: Guangdong Provincial Hospital of Chinese Medicine, Chinese University of Hong Kong.

Reporting Unit: Guangdong Provincial Hospital of Chinese Medicine

Research Director: [name]

Statistical Analysis Plan

Statistical analysis of our research will use SPSS 18.0 and MATLAB statistical software. The measurement data adopt T-Test, counting data use repeated measurement variance analysis and X2 test. And the image analysis adopt SPM8 software.

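### The SAP names no ordinal method and no adjustment for entry stage for Brunnstrom stage, and the plainest of its listed tests lose power as a result (minor)

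*Protocol*

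**What the plan says.** Section 5.6 of the protocol, under Secondary Outcome Measure, lists "Wolf Motor Function Test; Brunnstrom staging of upper limb movement; Fugl-Meyer Motor Assessment of upper limb; Modified Barthel Index". All four are assessed at three visits: "Time Frame: Before treatment, 2 weeks and 4 weeks after treatment, 3 times totally". Section 5.3, item 5, restricts entry by the same scale: "Brunnstrom stage of hemiplegic upper limb and hand is IV or V".

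The SAP's rule for clinical outcomes is one sentence: "The measurement data adopt T-Test, counting data use repeated measurement variance analysis and X2 test". It recognises two kinds of data and has no class for ordered categories. It does not say which kind Brunnstrom stage is, whether the quantity tested is the week-4 stage or the change from entry, or whether any baseline value is used. Section 5.2 says randomisation is stratified but names no factors, so entry stage cannot be assumed to be balanced by design.

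**The concern.** The analyst has to choose a test for Brunnstrom stage from a list that was not written for ordinal data, possibly after seeing the results. The options differ in what they use:

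- **Chi-square on week-4 stage** uses neither the order of the stages nor the stage at entry. It can also be significant because patients gather in a middle stage, without net improvement.
- **A t-test on week-4 stage** keeps the order, as equally spaced scores, but ignores the entry stage.
- **Repeated-measures ANOVA** keeps the order as scores and has the entry stage as its first visit. However, it tests an overall group-by-time interaction, and its group main effect is diluted by the pre-treatment visit.

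Patients who start at V have less room to move than those who start at IV, so the entry stage should explain much of the week-4 stage. Leaving it out discards information that the trial already collects.

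**Working it through.** **1. The plan's own figure.** The documents give no sample size or power for Brunnstrom stage. The only calculation is for FMA: mean 30, SD 10, alternative 37, so d = 7/10 = 0.7 ("The amount of effect between groups is ~ 0.7"; "If 0.8 of the statistical verification force is required"). Alpha is not stated; I take 0.05 two-sided. For a one-sample t-test, n ≈ (1.960 + 0.842)²/0.7² + 1.96²/2 = 16.02 + 1.92 = 17.9. The noncentral t gives 18.03, rounded up to 19, which reproduces the plan. With dropout, 19 × 1.15 = 21.85, rounded up to 22. I therefore use 19 completers and 22 enrolled per arm. That this is a one-sample form is a separate matter.

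**2. Assumptions not in the documents.** Two arms are compared, half the patients enter at IV and half at V, and week-4 stage is IV, V or VI. The effect is a common odds ratio (OR) of 3 or 5. Control probabilities of reaching at least V, and VI:

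| Pattern | Entered at IV | Entered at V |
|---|---|---|
| Typical | 0.50, 0.10 | 0.95, 0.35 |
| More stay | 0.30, 0.03 | 0.97, 0.20 |
| More move | 0.70, 0.20 | 0.97, 0.55 |

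**3. Simulated power, 19 per arm, 4,000 trials per row.**

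| Pattern, OR | Chi-square, week 4 | t-test, week 4 | t-test, change | ANCOVA | van Elteren by entry stage |
|---|---|---|---|---|---|
| Typical, 5 | 0.488 | 0.595 | 0.664 | 0.682 | 0.691 |
| More stay, 3 | 0.185 | 0.249 | 0.350 | 0.352 | 0.358 |
| More stay, 5 | 0.382 | 0.494 | 0.648 | 0.653 | 0.662 |
| More move, 3 | 0.230 | 0.326 | 0.344 | 0.378 | 0.373 |
| More move, 5 | 0.458 | 0.578 | 0.577 | 0.638 | 0.644 |

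Losses against van Elteren:
- Chi-square: from 0.373 − 0.230 = 0.14 to 0.662 − 0.382 = 0.28.
- t-test on week-4 stage: from 0.373 − 0.326 = 0.05 to 0.662 − 0.494 = 0.17.
- t-test on change: from 0.358 − 0.350 = 0.01 to 0.644 − 0.577 = 0.07.

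In a further run of the typical pattern at OR 5, a proportional-odds model adjusted for entry stage gave 0.73, with van Elteren at 0.69.

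**4. Repeated-measures ANOVA.** This also needs assumptions about week 2: half the log odds ratio, and a latent correlation of 0.7 with week 4. Group-by-time power (Greenhouse-Geisser) for typical, more stay and more move was 0.320, 0.304 and 0.264 at OR 3, and 0.584, 0.584 and 0.488 at OR 5. The losses run from 0.358 − 0.304 = 0.05 to 0.644 − 0.488 = 0.16. The group main effect reached only 0.11–0.16 at OR 3 and 0.20–0.29 at OR 5.

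**5. Where the gain comes from: a hand check (typical, OR 5).** Score the stages 0, 1, 2.
- Control means: 0.60 from IV and 1.30 from V; variances 0.44 and 0.31.
- Multiplying the odds by 5 gives treated means of 0.833 + 0.357 = 1.190 and 0.990 + 0.729 = 1.719; variances 0.488 and 0.223.
- Average gain: (0.590 + 0.419)/2 = 0.505.
- Variance within entry stage: (0.44 + 0.31 + 0.488 + 0.223)/4 = 0.365.
- Week-4 stage adds the spread between entry stages: ¼ × 0.70² = 0.1225 (control) and ¼ × 0.529² = 0.070 (treated), average 0.096, total 0.461.
- Change adds only ¼ × 0.30² = 0.0225 and ¼ × 0.471² = 0.055, average 0.039, total 0.404.

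With power ≈ Φ(0.505/√variance × √(19/2) − 2.03):
- week-4 stage: Φ(2.29 − 2.03) = 0.60
- change: Φ(2.45 − 2.03) = 0.66
- conditional on entry stage: Φ(2.58 − 2.03) = 0.71

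These agree with the simulated 0.60, 0.66 and 0.68–0.69. An unadjusted Wilcoxon test gave 0.60, the same as the t-test, so equal spacing is not what costs power here.

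**6. Twenty-two per arm.** For the typical pattern at OR 5: chi-square 0.56, week-4 t-test 0.66, van Elteren 0.74. A fourth control pattern (from IV, 60/35/5% at IV/V/VI; from V, 70/30% at V/VI) gave, at OR 3, 4 and 5: chi-square 23, 36, 48%; t-test 29, 46, 58%; van Elteren 42, 61, 74%. A repeat at OR 5 gave 44, 56 and 73%, so losses of 29 and 17 points.

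**7. Robustness.** With 30% or 70% entering at IV, the order of the methods did not change. Type I error was about 0.04–0.06 for every method.

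**The case against.** The strongest reply is that the defect is an unspecified quantity, not a weak family of tests. Objective 3.2 of the protocol speaks of changes in motor function. In the fourth pattern with 22 per arm, at OR 3, 4 and 5, a t-test on change gave 41, 61 and 72%, and so did chi-square on improved versus not improved; van Elteren gave 42, 62 and 74%. Two uses of listed tests thus come within about 2 points. This stands as a limit on the size of the point, but the SAP specifies neither use.

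A reader might infer several stronger claims that the documents or the checks do not support:

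- **Every listed test discards the order or the entry stage.** Repeated-measures ANOVA does neither, because the entry stage is its first visit. The SAP attaches it to counting data, though, so its use for Brunnstrom stage is not clearly planned.
- **The t-test fails because stages are not equally spaced.** A plain rank test has the same power. The loss comes from ignoring entry stage.
- **Sparse cells invalidate chi-square.** Expected counts below 5 are common: in the typical pattern with no effect, stage VI has (0.10 + 0.35)/2 × 19 = 4.3 per arm. But type I error was not inflated.
- **Only three values are possible.** The documents fix the entry stages. They do not state the top stage or rule out a fall below IV.

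It is also fair that the outcome is one of four secondary measures, and that at smaller effects all the tests are weak. At OR 2, chi-square, week-4 t-test and van Elteren gave 12, 14 and 20%.

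**Conclusion.** The point holds in a limited form. An ordinal secondary outcome has no ordinal method, no adjustment for entry stage and no assigned test. Against a test that conditions on entry stage, the loss is about 14–30 points for chi-square on week-4 stage, 5–17 for a t-test on week-4 stage, 5–16 for the group-by-time test and 1–7 for a t-test on change. The direction was the same in every scenario run, apart from negligible differences between ANCOVA and van Elteren.

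The sizes rest on the assumed entry mix, transition rates, three-value range and common odds ratio of 3–5, none of which is in the documents. Most of the gain comes from conditioning on entry stage; the ordinal form itself matters mainly in comparison with chi-square. Severity is minor: no power is claimed for this outcome, and the trial's primary outcomes are not affected.

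**What to change.** Add one sentence to the SAP:

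> *Brunnstrom stage at week 4 is compared between arms by a proportional-odds model with entry stage as covariate, reporting the common odds ratio and 95% CI for each pairwise arm comparison, with a van Elteren test stratified by entry stage if the model does not fit; week 2 is supportive.*

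This fixes the test, the quantity and the main time point before the data are seen. It does not settle multiplicity across the three pairwise comparisons, which should be decided together with the other outcomes.

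The cost is one sentence. No new data are needed, because the stage is already assessed at screening and before treatment.
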